7.5 Patients with uncontrolled myeloproliferation

For patients who have uncontrolled myeloproliferation, the concomitant use of hydroxycarbamide is permitted. Patients who are already receiving hydroxycarbamide therapy at the time of trial entry will be allowed to continue hydroxycarbamide at the time of initiation of tefinostat treatment. The introduction of hydroxycarbamide is also permitted, at the discretion of local investigators, for WBC persistently $\geq 30 \times 10^9 / l$. Investigators should make every effort, according to individual patient circumstances, to wean and stop hydroxycarbamide as patients continue on tefinostat therapy. The concomitant use of hydroxycarbamide will not be permitted following completion of the third cycle of tefinostat (week 12) and patients with uncontrolled myeloproliferation beyond this time point will be withdrawn from the study.

7.6 Tefinostat dose modifications

Tefinostat dose adjustments (both escalations and reductions) will be made for purposes of safety and clinical efficacy. All dose changes should be recorded in the CRF. Investigators should maintain a low threshold for discussing planned dose changes with the chief investigator or trial management team.

7.6.1 Dose reductions for toxicities related to tefinostat

Toxicities will be graded using the NCI CTCAE version 4 (Appendix 8).

No modification in tefinostat dose is required for grade 1-2 toxicities.

In the event of grade 3 or 4 toxicity considered possibly, probably or definitely related to tefinostat, the study drug should be temporarily discontinued and the next treatment cycle delayed until the toxicity has resolved to grade 1 or less. Thereafter, the drug should be recommenced at a dose reduced by one dose level (120mg/day); patients previously taking 360mg should be reduced to 240mg, patients taking 240mg should be reduced to 120mg. The lowest permitted tefinostat dose is 120mg daily. Attempts to re-escalate the tefinostat dose following resolution of toxicity will be at the discretion of the investigator, but should not be made until the patient has completed a full 28-day cycle at the reduced dose without additional grade 3-4 toxicity; if the same AE occurs a second time further dose escalations will not be permitted.

If a grade 3 or 4 toxicity considered related to tefinostat does not resolve to grade 1 or less within 28 days, the patient will be removed from the study but should continue to undergo follow-up evaluations (please refer to section 8.5 for patient evaluations required in these circumstances).

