During a 28-day oral toxicity study in monkeys, males treated at 450mg/kg/day showed dehydration, whilst both males and females at this dose level showed a slight reduction in body weight, with recovery evident during the 28-day recovery period. As in the rat, there was evidence of a reversible, regenerative anaemia in all treated groups. Platelet count was increased for males and females treated at 150 and 450mg/kg/day and activated partial thromboplastin times were longer for animals treated at 450mg/kg/day. There was recovery from these changes following cessation of dosing. A decrease in lymphocytes in animals dosed at 450mg/kg/day was noted at the end of the treatment period. Although this was not statistically significant, it was still evident at the end of the 28-day recovery period. Clinical chemistry changes noted included increased total bilirubin (all dose levels), increased urea (females, all dose levels) increased aspartate aminotransferase, alanine aminotransferase and lactate dehydrogenase (450mg/kg/day), decreased cholesterol (150 and 450mg/kg/day) and increased creatinine (150 and 450mg/kg/day). Decreased thymus weight was apparent at the end of the treatment period for all dose levels and was still evident at the end of the 28-day recovery period for females. Moderate or marked thymic atrophy was noted at 450mg/kg/day with mild atrophy evident for individual animals dosed at 50 and 150mg/kg/day. This finding was still evident in females at a reduced severity on completion of the 28day recovery period. Accumulation of haemosiderin (mild or moderate) in Kupffer cells was present in the liver of animals treated at 450mg/kg/day and females at 150mg/kg/day with minimal accumulation observed sporadically in the remaining treatment groups. The finding was still evident in females at a reduced severity on completion of the 28-day recovery period. Minimal or mild centrilobular hepatocyte hypertrophy or minimal or mild hepatocyte degeneration was evident for individual animals at 150 and 450mg/kg/day. These findings were not evident at the end of the 28-day recovery period. Mild periportal fatty vacuolation was observed at the end of the 28-day recovery period in one animal of each sex previously dosed at 450mg/kg/day. A NOAEL could not be defined for this study.

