5.1 Inclusion Criteria

Patients will be eligible for the MONOCLE study if **all** of the following apply:

1. Newly-diagnosed or previously-treated CMML meeting WHO criteria (Appendix 1) with the following characteristics:

All CMML-2 patients are eligible.

For patients classified as CMML-1, the following must be present:

· Symptomatic bone marrow failure or myeloproliferation defined as one or more of:

red cell transfusion dependence with pre-transfusion Hb <90g/I

symptomatic anaemia (Hb <115g/l)

thrombocytopenia (platelets <50 x 10⁹/l)

symptomatic bleeding due to platelet function defect or DIC/fibrinolysis

white blood cell count >50 x 109/l

and/or

· CMML-specific Prognostic Score (CPSS) of intermediate-2 or high risk (11) (see Appendix 2 for derivation of CPSS score)

and/or

- · Systemic symptoms including weight loss with no alternative explanation (10% of baseline weight within previous 6 months)
- · Symptomatic splenomegaly
- · Symptomatic extramedullary involvement, e.g. skin infiltration, serous effusions
- 2. Subject is able and willing to sign the Informed Consent Form
- 3. Age greater than or equal to 18 years at the time of signing the Informed Consent Form
- 4. Willingness to undergo scheduled assessments as per the study protocol including stipulated bone marrow assessments
- 5. ECOG performance status of 0-2 at study entry (see Appendix 6)
- 6. Women of childbearing potential must have a negative urine pregnancy test within 7 days prior to starting study drug

- 7. Women of childbearing potential must use at least two effective contraceptive methods throughout the study and for three months following the date of the last dose of study drug (see Appendix 7)
- 8. Men whose partner is a woman of childbearing potential must use at least two effective contraceptive methods (see Appendix 7)

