5.2 Exclusion Criteria

Patients will not be eligible for the MONOCLE study if *any* of the following apply:

- 1. CMML with eosinophilia and 5q33 abnormality
- 2. CMML patients who are considered suitable for allogenic stem cell or bone marrow transplantation
- 3. Previous chemotherapy for CMML except Hydroxycarbamide and 5-azacitidine
- 4. Creatinine concentration > 2x the upper limit of institutional normal range
- 5. Liver transaminases (AST / ALT) > 3x the upper limit of institutional normal range or serum bilirubin > 4x the upper limit of institutional normal range
- 6. Pregnant or lactating females
- 7. Use of experimental drug or therapy within 28 days of registration
- 8. Other malignancy within the last 3 years other than: curatively-treated basal cell or squamous cell skin cancer, carcinoma in situ of the cervix, organ-confined or treated non-metastatic prostate cancer with negative prostate-specific antigen, in situ breast carcinoma after complete surgical resection, or superficial transitional cell bladder carcinoma. Cases of CMML seen in association with systemic mastocytosis (systemic mastocytosis with associated clonal haematological non-mast cell lineage disease) should be discussed with the Chief Investigator and may be included if the CMML is considered to be the clinically predominant disease.
- 9. Known seropositivity for HIV infection or infectious hepatitis (type B or C)
- 10. Uncontrolled inter-current illness including, but not limited to, ongoing infection, psychiatric illness or social situation that the treating physician judges would limit compliance with study requirements

All queries relating to eligibility criteria should be directed to the Chief Investigator via Centre for Trials Research , Cardiff University (see contact details at front of protocol)

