7.4 Tefinostat dosing and treatment schedule

Tefinostat will be administered orally once daily on a continuous basis. Patients will commence tefinostat at a once daily dose of 360mg (i.e. 3 x 120mg tefinostat capsules). Treatment cycles will be defined as 28 days (4 weeks) in length for the purposes of scheduling study procedures and response evaluations. The dose of tefinostat may be escalated or de-escalated at the investigator's discretion for reasons of safety and clinical efficacy (see section 7.6).

Tefinostat capsules should be ingested with a sufficient quantity of water, preferably following a meal. In the event of a delayed dose patients may take the dose up to 6 hours after the scheduled dose time. If a dose is more than 6 hours late, the dose should be missed and the patient should continue with the next dose at the scheduled time. If a patient vomits following a dose, the dose should not be replaced.

Cycles of tefinostat therapy will be repeated every 28 days for at least 6 cycles unless the patient withdraws their consent for the study, disease progression or loss of response occurs (see Appendix 3) or therapy is stopped on grounds of tolerability.

Following completion of the sixth cycle of treatment patients will undergo a formal response assessment (see section 8.3). Responding patients, defined as: clinical benefit or better by International Consortium MDS/MPN Response Criteria (Appendix 3) may continue taking tefinostat until loss of response, disease progression or the development of unacceptable toxicity. Immediately upon completion of the sixth cycle a short extension of tefinostat therapy (maximum 14 days) will be permitted in order to allow adequate time for sites to fully assess week 24 response assessment investigations.

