8.1.5 Haematology assessments

- Full blood count to include haemoglobin, differential white cell count (including monocyte count and blast %), platelet count, MCV
- Reticulocyte count
- Coagulation screen to include APTT, PT, fibrinogen
- Bone marrow aspiration and trephine biopsy. Analysis of bone marrow aspirate to include morphological assessment
 (with differential count), local immunophenotypic (to include blast and typical / atypical monocytoid populations) and
 cytogenetic assessments. Local assessment of trephine histology.

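### Section 7.6.1 has no return-to-baseline option, so a patient who enters cytopenic can be taken off tefinostat although the count is back at its entry value

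*Protocol*

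**What the plan says.** Section 7.6.1 of the protocol grades toxicity by CTCAE version 4. For a grade 3-4 toxicity judged possibly, probably or definitely related, "the study drug should be temporarily discontinued and the next treatment cycle delayed until the toxicity has resolved to grade 1 or less". Treatment then resumes one dose level lower. If a related grade 3-4 toxicity "does not resolve to grade 1 or less within 28 days, the patient will be removed from the study"; the same sentence keeps follow-up evaluations going, so removal means coming off treatment. The rule is not limited to non-haematological toxicity, and neither sentence offers recovery to baseline as an alternative.

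Section 5.1 makes cytopenia a reason for entry in CMML-1. The qualifying features include "thrombocytopenia (platelets <50 x 10⁹/l") and "red cell transfusion dependence with pre-transfusion Hb" below 90 g/l. All CMML-2 patients qualify whatever their counts. Section 5.2 ("Patients will not be eligible for the MONOCLE study if" any of ten criteria applies) limits creatinine, transaminases and bilirubin but no blood count. Section 7.4 gives everyone the same start: "Patients will commence tefinostat at a once daily dose of 360mg".

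**The concern.** The restart condition is a fixed grade, but some patients enter with a count already worse than that grade. If such a count falls further, and the fall reaches or stays within grade 3-4 and is thought possibly due to tefinostat, the patient has to rise above the entry count to resume. Full recovery to the level at which the protocol allowed 360mg does not permit 240mg. After 28 days the patient is off treatment.

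What is at stake is treatment for the individual patient and, through that, the chance to show a response. Section 10.4.1 reads response at the sixth or last cycle, whichever is earlier. Appendix 3 wants blood-count benefit shown over at least 8 weeks, and section 10.1 treats anyone not known to have responded as a non-responder, without replacement.

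**Working it through.** No figure in the protocol is in dispute here. The check has three parts: does the rule cover blood counts, how large is the gap, and would a baseline clause still work as a hold.

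**Coverage.** The primary safety endpoint (10.4.1) and the toxicity items in the SAE definition (11.1.3) both say non-haematological. Section 7.6.1 does not. Section 11.1.1 counts a new, clinically relevant laboratory deterioration as an adverse event, and 11.1.4 recognises haematological toxicity as a class. The advice in 7.6 to discuss dose changes with the chief investigator grants no exception, and sections 8.5, 8.6 and 11 contain no baseline rule. Blood counts are therefore covered.

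**Gap.** The protocol names CTCAE version 4 but does not print its thresholds, so the grade 1 floors are assumptions: platelets 75 x10⁹/l (range 50 to 100) and haemoglobin 100 g/l (range 90 to 110). The entry values are illustrative counts allowed by 5.1.

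Rise above entry needed to restart = grade 1 floor − entry count.

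| Platelets at entry | Floor 50 | Floor 75 | Floor 100 |
|---|---|---|---|
| 20 | 30 | 55 | 80 |
| 30 | 20 | 45 | 70 |
| 40 | 10 | 35 | 60 |
| 49 | 1 | 26 | 51 |

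| Haemoglobin at entry (g/l) | Floor 90 | Floor 100 | Floor 110 |
|---|---|---|---|
| 70 | 20 | 30 | 40 |
| 80 | 10 | 20 | 30 |
| 89 | 1 | 11 | 21 |

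The sign is positive for any platelet floor of 50 or more and any haemoglobin floor of 90 or more. That follows directly from the entry cut-offs in 5.1. It shows the direction of the problem, not how often it occurs.

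For scale, Appendix 3 counts a platelet rise of at least 30, from a start of 20-100, towards clinical benefit (subject to its 8-week condition). At a floor of 75, entry at 45 needs 75 − 45 = 30 and entry at 21 needs 75 − 21 = 54. Anyone entering at 21 to 45 therefore needs a rise of response size, off drug, merely to resume.

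The haemoglobin figures are gaps in the measured value, not required marrow recovery. Section 7.7.1 permits transfusion and 7.6.1 does not ask for transfusion-free recovery, so transfusion can usually close that gap.

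**Does a baseline clause still hold the drug?** Take the target as the pre-treatment value if it is below 75, and 75 otherwise (platelets, floor 75 assumed).

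| Pre-treatment | Lowest count | Current target | Target with clause | Still a hold? |
|---|---|---|---|---|
| 49 | 30 | 75 | 49 | yes |
| 40 | 15 | 75 | 40 | yes |
| 20 | 8 | 75 | 20 | yes |
| 60 | 30 | 75 | 60 | yes |
| 90 | 40 | 75 | 75 | yes |

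Using the value rather than the grade keeps the hold real even for a fall within one grade. A patient who enters at 90 is unaffected.

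**The case against.** The strongest reply is that 7.6.1 speaks of the toxicity resolving, not the count. Under 11.1.1 a laboratory adverse event is a new deterioration, so a count back at its entry value leaves only CMML and the toxicity has resolved. An investigator might act on that reading. But 7.6.1 asks for a CTCAE grade, which is taken here to be an absolute level, and nothing in the protocol says that return to entry counts as grade 1. The reading lowers confidence and shows that sites could differ; it does not repair the text.

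Second, the evidence for a drug-related fall is thin, and this stands. Appendix 12 reports that the class's dose-limiting thrombocytopenia was not seen and that creatinine and magnesium were the only potentially dose-related laboratory signals. Monkey platelets rose. Section 11.1.4 lists grade 4 haematological toxicity as expected from CMML, which makes attribution to tefinostat less likely. The case is still not excluded. In the monkey study "there was evidence of a reversible, regenerative anaemia in all treated groups", rats showed anaemia at 300mg/kg/day, Appendix 11 asks for monitoring of haematological toxicity, and the clinical data come from 18 patients, with firm tolerability conclusions only up to 320mg.

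Third, a strict rule may suit a drug with two CMML patients of prior experience, and a patient who has just had a possibly related fall is not the same risk as one who has not. That is fair. However, the dose reduction already answers it, and the protocol accepted the same count for a higher dose.

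Fourth, a baseline value is not unique: counts are taken at screening and on day 1, and transfusion may distort either. This is correct, and the fix has to define the value.

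**Conclusion.** The point holds as a gap in wording that affects individual patients. Followed literally, 7.6.1 takes a patient off tefinostat at 28 days although the count has returned to the level at which full dose was started. It matters mainly for platelets and other counts that transfusion cannot readily correct. It rests on absolute CTCAE grading, on assumed grade 1 floors, and on a fall judged at least possibly related.

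A reader might infer more, but the documents do not support it:
- Cytopenic patients are not removed automatically. An unchanged entry cytopenia is no new deterioration under 11.1.1 and triggers nothing.
- No loss of power can be claimed. The protocol gives no basis for a removal rate, and the number affected is probably small.
- The primary safety endpoint is not inflated, because 10.4.1 counts grade 3-4 toxicity only when it is non-haematological.
- Patients are not lost to follow-up; 7.6.1 keeps it going.

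Severity is minor, confidence moderate. It is worth making because it is cheap.

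**What to change.** In both the restart and the removal sentence of 7.6.1, let the condition read: *resolved to grade 1 or less or, for a blood count already worse than grade 1 before treatment, returned to at least the patient's pre-treatment value*.

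Define that value as the mean of the screening and cycle 1 day 1 pre-dose counts not influenced by transfusion, or the single such count if only one exists. If neither qualifies, the present rule stands. Require the recovery count also to be free of transfusion influence when the baseline route is used. Appendix 5 already takes a similar approach to pre-treatment counts for the IWG criteria. Keep the one-level dose reduction and the 28-day limit.

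The cost is one clause and one definition in an amendment. No visit or test is added: section 8.1.5 already requires "Full blood count to include haemoglobin, differential white cell count" and platelets at baseline, 8.2.2 repeats the counts on days 1 and 15 of each cycle, and transfusions and dose changes are already recorded. Sites would need to draw the day 1 count before the first dose, and the clinical team must say when a count is influenced by transfusion. The downside is that a few cytopenic patients restart, at a reduced dose, at counts worse than grade 1, but not below their entry level so defined.

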7.6.2 Dose escalations for clinical efficacy

The dose of tefinostat may be increased by one dose level (120mg/day) up to a maximum daily permitted dose of 480mg for patients who have not achieved a maximal clinical response (see Appendix 3). Dose increases may be made at the start of a new 4-week cycle of tefinostat therapy in the absence of significant ongoing toxicity. The earliest permitted time for dose increase will be the beginning of treatment cycle 2 (week 5). The dose of tefinostat should not be increased to a higher level if the patient previously required a safety-related dose reduction.

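### Sections 7.6.1 and 7.6.2 can be read to give opposite instructions on raising the tefinostat dose after a toxicity-related reduction, and the protocol does not say which reading is meant.

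*Protocol*

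**What the plan says.** Section 7.6.1 (dose reductions for tefinostat-related toxicity) has the drug stopped for a related grade 3 or 4 toxicity and restarted one level (120mg/day) lower once the toxicity has resolved to grade 1 or less. It then allows the dose to go back up: "Attempts to re-escalate the tefinostat dose following resolution of toxicity will be at the discretion of the investigator". Such attempts "should not be made until the patient has completed a full 28-day cycle at the reduced dose without additional grade 3-4 toxicity". The only permanent bar is that "if the same AE occurs a second time further dose escalations will not be permitted".

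Section 7.6.2 (escalations for clinical efficacy) allows increases of one level at the start of a new cycle, from cycle 2 at the earliest, "up to a maximum daily permitted dose of 480mg for patients who have not achieved a maximal clinical response". It ends: "The dose of tefinostat should not be increased to a higher level if the patient previously required a safety-related dose reduction".

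The surrounding text does not arbitrate. Section 7.4 says the dose "may be escalated or de-escalated at the investigator's discretion for reasons of safety and clinical efficacy" and points to section 7.6. The opening of section 7.6 asks for all dose changes to be recorded in the CRF and for a low threshold for discussing planned changes with the chief investigator or trial management team.

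**The concern.** Both sections govern the same patient: one whose dose was lowered for toxicity and who has since recovered. Section 7.6.1 gives conditions under which the dose may rise again. The closing sentence of section 7.6.2 has no condition, exception or cross-reference, and it does not say what the higher level is higher than. A site that relies on one section can act in the opposite way to a site that relies on the other, and each can point to the protocol.

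This is first a matter of patient safety, because the instruction concerns people who have had a related grade 3-4 toxicity. It also matters for interpretation. In a single-arm trial of up to 40 patients there is no control arm against which differences in dosing between sites would balance out. Dose after recovery contributes to exposure before the response assessment, to time on drug and to later adverse events.

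**Working it through.** The protocol gives no figure to reproduce here. The check is a comparison of texts, followed by the timing and a rough count.

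**1. One patient under both sections.** The dose levels are those in section 7.6.1. A patient on 360mg has a related grade 3 toxicity, recovers, restarts at 240mg, completes 28 days without further grade 3-4 toxicity, and has not reached a maximal response.

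- Section 7.6.1: an increase is at the investigator's discretion.
- Section 7.6.2, literal reading (above the current, reduced dose): an increase should not be made.
- Section 7.6.2, alternative reading (above the pre-toxicity dose): a return to 360mg is not barred, but going beyond 360mg is.

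**2. Does the wording choose between the readings?**

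- For the alternative reading: the two headings separate toxicity from efficacy. In addition, if every increase after a reduction were barred, the clean-cycle condition and the second-occurrence bar in section 7.6.1 would have nothing to act on.
- For the literal reading: section 7.6.2 itself describes an increase as one 120mg step, which is naturally a step from the current dose, and it never mentions the pre-toxicity dose.
- A case at the maximum: a patient raised to 480mg for efficacy is reduced by one level, 480 − 120 = 360mg. Going back to 480mg is a re-escalation under section 7.6.1 and also an increase under section 7.6.2. On the alternative reading the closing sentence has no effect for this patient, because 480mg is already the ceiling.

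Each reading leaves some part of the text without effect, so the wording does not decide the matter.

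**3. When can the difference arise?** Section 7.6.1 requires the toxicity to resolve and then one full cycle at the reduced dose. After an event in cycle 1, the reduced-dose cycle is cycle 2 at the earliest, so re-escalation starts at cycle 3 at the earliest. The primary safety endpoint (section 10.4.1) covers only the first two cycles. A patient whose own event qualifies for that endpoint has also been counted already.

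Response is assessed at day 29 of the sixth or last cycle (section 10.4.1). Under the two readings, dosing can therefore differ over cycles 3 to 6 at most:

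- duration: 4 cycles × 28 days = 112 days;
- difference for the patient in step 1: 360 − 240 = 120mg/day, and 120/240 = 50% of the reduced dose.

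This is the longest window for one such patient. It is not an average over the trial.

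**4. How many patients?** Section 10.1 uses 20% as the acceptable toxicity rate and 40% as the unacceptable rate. With 40 patients, 0.20 × 40 = 8 and 0.40 × 40 = 16. These are rough counts of patients with a qualifying non-haematological toxicity or related death in the first two cycles. They are not counts of patients handled differently.

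- They include deaths, patients removed because the toxicity did not resolve within 28 days, and patients whom no investigator would re-escalate.
- They leave out later events and haematological grade 3-4 events, which also lead to a reduction under section 7.6.1.
- The figure of 16 also assumes that all 40 patients are enrolled. Stage 1 continues only with 6 or fewer toxicities in 19, and at a true rate of 40% the probability of 7 or more in 19 (binomial) is 0.69.

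**The case against.** The best defence is that the sections deal with different things. Section 7.6.1 concerns going back up after a reduction, and section 7.6.2 concerns going beyond the previous dose in search of a better response. The headings and the choice of verbs fit this, and it gives the detailed rule in section 7.6.1 something to do. Section 7.6 also routes planned dose changes towards the chief investigator or trial management team and has every change recorded, which makes divergent handling less likely and traceable. Finally, only patients who have recovered and completed a clean cycle can be re-escalated, and then only by choice.

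Much of this stands. The compatible reading is plausible and somewhat favoured by the structure. A reader might infer that section 7.6.2 flatly forbids any increase and so plainly contradicts section 7.6.1; that is the literal reading but not the only one. The compatible reading nevertheless depends on words that the protocol does not contain, and it leaves the sentence without effect for a patient reduced from 480mg. The advice to discuss dose changes helps only a site that sees the question. A site that finds its own section clear has little reason to ask.

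**Conclusion.** The point holds as an unresolved ambiguity in a safety instruction: one reading contradicts section 7.6.1, the other does not, and the protocol does not choose. It should be corrected.

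Its reach is limited to safety after a related grade 3-4 toxicity, dose exposure before the cycle 6 response assessment (and so possibly the response co-primary), duration of therapy, and later toxicity. Two stronger inferences are not supported:

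- That both co-primary outcomes are affected. Re-escalation falls after the first two cycles, so the primary safety endpoint is not materially touched. This rests on reading the clean 28 days as a full treatment cycle that follows the one in which the event occurred.
- That 8 to 16 patients would be managed inconsistently. The number cannot be derived from the protocol. It depends on how many patients recover, whether investigators wish to re-escalate, and how sites read the sentence, and the protocol gives none of these. No size of effect on the response rate can be given either.

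**What to change.** Reconcile sections 7.6.1 and 7.6.2 in one statement that (a) names the reference dose for the higher level in section 7.6.2, and (b) says whether that sentence limits the re-escalation in section 7.6.1 or is separate from it. The statement should also cover a patient reduced from the 480mg maximum, so that it has a clear meaning at every dose level. A cross-reference in each section would keep the two together. Which rule applies is for the clinical team to decide; this review takes no position on it.

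The cost is about one sentence in a protocol amendment and a note to sites. Sample size, endpoints and analysis do not change. Dose changes are already recorded in the CRF, so any re-escalation before the clarification can be identified and described.
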